14.1.2.4.3 Determination of non-target lesion response

Table 14-2 Response criteria for non-target lesions

Response Criteria	Evaluation of non-target lesions
Complete Response (CR):	Disappearance of all non-target lesions. In addition, all lymph nodes assigned a non-target lesions must be non-pathological in size (< 10 mm short axis)
Progressive Disease (PD):	Unequivocal progression of existing non-target lesions. ¹
Non-CR/Non-PD:	Neither CR nor PD
Unknown (UNK)	Progression has not been documented and one or more non-target lesions have not been assessed or have been assessed using a different method than baseline ² .

1. The assignment of PD solely based on change in non-target lesions in light of target lesion response of CR, PR or SD should be exceptional. In such circumstances, the opinion of the investigator or central reviewer does prevail.

2. It is recommended that the investigator and/or central reviewer should use expert judgment to assign a Non-UNK response wherever possible (see notes section for more details)

Notes on non-target lesion response

- The investigator and/or central reviewer can use expert judgment to assign a non-UNK response wherever possible, even where lesions have not been fully assessed or a different method has been used. In many of these situations it may still be possible to identify equivocal progression (PD) or definitively rule this out (non-CR/Non-PD) based on the available information. In the specific case where a more sensitive method has been used indicating the absence of any non-target lesions, a CR response can also be assigned.
- The response for non-target lesions is **CR** only if all non-target non-nodal lesions which were evaluated at baseline are now all absent and with all non-target nodal lesions returned to normal size (i.e. < 10 mm). If any of the non-target lesions are still present, or there are any abnormal nodal lesions (i.e. ≥ 10 mm) the response can only be ‘**Non-CR/Non-PD**’ unless there is unequivocal progression of the non-target lesions (in which case response is **PD**) or it is not possible to determine whether there is unequivocal progression (in which case response is UNK).
- Unequivocal progression: To achieve “unequivocal progression” on the basis of non-target disease there must be an overall level of substantial worsening in non-target disease such that, even in presence of CR, PR or SD in target disease, the overall tumor burden has increased sufficiently to merit discontinuation of therapy. A modest “increase” in the size of one or more non-target lesions is usually not sufficient to qualify for unequivocal progression status. The designation of overall progression solely on the basis of change in non-target disease in the face of CR, PR or SD of target disease is therefore expected to be rare. In order for a PD to be assigned on the basis of non-target lesions, the increase in the extent of the disease must be substantial even in cases where there is no measurable disease at baseline. If there is unequivocal progression of non-target lesion(s), then at least one of the non-target lesions must be assigned a status of “Worsened”. Where possible, similar rules to those described in [Section 14.1.2.4.2](#) for assigning PD following a CR for the non-target lesion response in the presence of non-target lesions nodal lesions should be applied.

14.1.2.4.4 New lesions

The appearance of a new lesion is always associated with Progressive Disease (PD) and has to be recorded as a new lesion in the New Lesion eCRF page.

- If a new lesion is **equivocal**, for example because of its small size, continued therapy and follow-up evaluation will clarify if it represents truly new disease. If repeat scans confirm there is definitely a new lesion, then progression should be declared using the date of the first observation of the lesion
- If new disease is observed in a region which was **not scanned at baseline** or where the particular baseline scan is not available for some reason, then this should be considered as a PD. The one exception to this is when there are no baseline scans at all available for a patient in which case the response should be UNK, as for any of this patient's assessment (see [Section 14.1.2.5](#)).
- A **lymph node is considered as a “new lesion”** and, therefore, indicative of progressive disease if the short axis increases in size to ≥ 10 mm for the first time in the study plus 5 mm absolute increase. **FDG-PET:** can complement CT scans in assessing progression (particularly possible for ‘new’ disease). See [Section 14.1.2.2](#).

14.1.2.5 Evaluation of overall lesion response

The evaluation of overall lesion response at each assessment is a composite of the target lesion response, non-target lesion response and presence of new lesions as shown below in [Table 14-3](#).

Table 14-3 Overall lesion response at each assessment

Target lesions	Non-target lesions	New Lesions	Overall lesion response
CR	CR	No	CR ¹
CR	Non-CR/Non-PD ³	No	PR
CR, PR, SD	UNK	No	UNK
PR	Non-PD and not UNK	No	PR ¹
SD	Non-PD and not UNK	No	SD ^{1,2}
UNK	Non-PD or UNK	No	UNK ¹
PD	Any	Yes or No	PD
Any	PD	Yes or No	PD
Any	Any	Yes	PD

1. This overall lesion response also applies when there are no non-target lesions identified at baseline.

2. Once confirmed PR was achieved, all these assessments are considered PR.

3. As defined in [Section 14.1.2.4](#).

If there are no baseline scans available at all, then the overall lesion response at each assessment should be considered Unknown (UNK).

In some circumstances it may be difficult to distinguish residual disease from normal tissue. When the evaluation of complete response depends on this determination, it is recommended that the residual lesion be investigated (fine needle aspirate/biopsy) to confirm the CR.

14.1.3 Efficacy definitions

The following definitions primarily relate to patients who have measurable disease at baseline. [Section 14.1.3.2.8](#) outlines the special considerations that need to be given to patients with no measurable disease at baseline in order to apply the same concepts.

14.1.3.1 Best overall response

The best overall response is the best response recorded from the start of the treatment until disease progression/recurrence (taking as reference for PD the smallest measurements recorded since the treatment started). In general, the patient's best response assignment will depend on the achievement of both measurement and confirmation criteria.

[figure not shown]
The best overall response will usually be determined from response assessments undertaken while on treatment. However, if any assessments occur after treatment withdrawal the protocol should specifically describe if these will be included in the determination of best overall response and/or whether these additional assessments will be required for sensitivity or supportive analyses. As a default, any assessments taken more than 30 days after the last dose of study treatment will not be included in the best overall response derivation. If any alternative cancer therapy is taken while on study any subsequent assessments would ordinarily be excluded from the best overall response determination. If response assessments taken after withdrawal from study treatment and/or alternative therapy are to be included in the main endpoint determination, then this should be described and justified in the protocol.

Where a study requires confirmation of response (PR or CR), changes in tumor measurements must be confirmed by repeat assessments that should be performed not less than 4 weeks after the criteria for response are first met.

Longer intervals may also be appropriate. However, this must be clearly stated in the protocol. The main goal of confirmation of objective response is to avoid overestimating the response rate observed. In cases where confirmation of response is not feasible, it should be made clear when reporting the outcome of such studies that the responses are not confirmed.

- For non-randomized trials where response is the primary endpoint, confirmation is needed.
- For trials intended to support accelerated approval, confirmation is needed
- For all other trials, confirmation of response may be considered optional.

The best overall response for each patient is determined from the sequence of overall (lesion) responses according to the following rules:

- CR = at least two determinations of CR at least 4 weeks apart before progression where confirmation required or one determination of CR prior to progression where confirmation not required
 - PR = at least two determinations of PR or better at least 4 weeks apart before progression (and not qualifying for a CR) where confirmation required or one determination of PR prior to progression where confirmation not required
 - SD = at least one SD assessment (or better) > 12 weeks after randomization/start of treatment (and not qualifying for CR or PR).
 - PD = progression ≤ 12 weeks after randomization/ start of treatment (and not qualifying for CR, PR or SD).
- 

- UNK = all other cases (i.e. not qualifying for confirmed CR or PR and without SD after more than 12 weeks or early progression within the first 12 weeks)

The time durations specified in the SD/PD/UNK definitions above are defaults based on a 8 week tumor assessment frequency. However these may be modified for specific indications which are more or less aggressive. In addition, it is envisaged that the time duration may also take into account assessment windows. E.g., if the assessment occurs every 6 weeks with a time window of ± 7 days, a BOR of SD would require a SD or better response longer than 5 weeks after randomization/start of treatment.

Overall lesion responses of CR must stay the same until progression sets in, with the exception of a UNK status. A patient who had a CR cannot subsequently have a lower status other than a PD, e.g., PR or SD, as this would imply a progression based on one or more lesions reappearing, in which case the status would become a PD.

Once an overall lesion response of PR is observed (which may have to be a confirmed PR depending on the study) this assignment must stay the same or improve over time until progression sets in, with the exception of an UNK status. However, in studies where confirmation of response is required, if a patient has a single PR ($\geq 30\%$ reduction of tumor burden compared to baseline) at one assessment, followed by a $< 30\%$ reduction from baseline at the next assessment (but not $\geq 20\%$ increase from previous smallest sum), the objective status at that assessment should be SD. Once a confirmed PR was seen, the overall lesion response should be considered PR (or UNK) until progression is documented or the lesions totally disappear in which case a CR assignment is applicable. In studies where confirmation of response is not required after a single PR the overall lesion response should still be considered PR (or UNK) until progression is documented or the lesion totally disappears in which case a CR assignment is applicable.

Example: In a case where confirmation of response is required the sum of lesion diameters is 200 mm at baseline and then 140 mm - 150 mm - 140 mm - 160 mm - 160 mm at the subsequent visits. Assuming that non-target lesions did not progress, the overall lesion response would be PR - SD - PR - PR - PR. The second assessment with 140 mm confirms the PR for this patient. All subsequent assessments are considered PR even if tumor measurements decrease only by 20% compared to baseline (200 mm to 160 mm) at the following assessments.

If the patient progressed but continues study treatment, further assessments are not considered for the determination of best overall response.

Note: these cases may be described as a separate finding in the CSR but not included in the overall response or disease control rates.

The best overall response for a patient is always calculated, based on the sequence of overall lesion responses. However, the overall lesion response at a given assessment may be provided from different sources:

- Investigator overall lesion response
- Central Blinded Review overall lesion response
- Novartis calculated overall lesion response (based on measurements from either Investigator or Central Review)

The primary analysis of the best overall response will be based on the sequence of investigator/central blinded review/calculated (investigator)/calculated (central) overall lesion responses.

Based on the patients' best overall response during the study, the following rates are then calculated:

Overall response rate (ORR) is the proportion of patients with a best overall response of CR or PR. This is also referred to as 'Objective response rate' in some protocols or publications.

Disease control rate (DCR) is the proportion of patients with a best overall response of CR or PR or SD. The objective of this endpoint is to summarize patients with signs of "activity" defined as either shrinkage of tumor (regardless of duration) or slowing down of tumor growth.

Clinical benefit rate (CBR) is the proportion of patients with a best overall response of CR or PR, or an overall lesion response of SD or Non-CR/Non-PD which lasts for a minimum time duration (with a default of at least 24 weeks in breast cancer studies). This endpoint measures signs of activity taking into account duration of disease stabilization.

Another approach is to summarize the progression rate at a certain time point after baseline. In this case, the following definition is used:

Early progression rate (EPR) is the proportion of patients with progressive disease within 8 weeks of the start of treatment.

The protocol should define populations for which these will be calculated. The timepoint for EPR is study specific. EPR is used for the multinomial designs of [Dent and Zee \(2001\)](#) and counts all patients who at the specified assessment (in this example the assessment would be at 8 weeks \pm window) do not have an overall lesion response of SD, PR or CR. Patients with an unknown (UNK) assessment at that time point and no PD before, will not be counted as early progressors in the analysis but may be included in the denominator of the EPR rate, depending on the analysis population used. Similarly when examining overall response and disease control, patients with a best overall response assessment of unknown (UNK) will not be regarded as "responders" but may be included in the denominator for ORR and DCR calculation depending on the analysis population (e.g., populations based on an ITT approach).

14.1.3.2 Time to event variables

The protocol should state which of the following variables is used in that study.

14.1.3.2.1 Progression-free survival

Usually in all Oncology studies, patients are followed for tumor progression after discontinuation of study medication for reasons other than progression or death. If this is not used, e.g., in Phase I or II studies, this should be clearly stated in the protocol. Note that randomized trials (preferably blinded) are recommended where PFS is to be the primary endpoint.

Progression-free survival (PFS) is the time from date of randomization/start of treatment to the date of event defined as the first documented progression or death due to any cause. If a

patient has not had an event, progression-free survival is censored at the date of last adequate tumor assessment.

PFS rate at x weeks is an additional measure used to quantify PFS endpoint. It is recommended that a Kaplan Meier estimate is used to assess this endpoint.

14.1.3.2.2 Overall survival

All patients should be followed until death or until patient has had adequate follow-up time as specified in the protocol whichever comes first. The follow-up data should contain the date the patient was last seen alive / last known date patient alive, the date of death and the reason of death (“Study indication” or “Other”).

Overall survival (OS) is defined as the time from date of randomization/start of treatment to date of death due to any cause. If a patient is not known to have died, survival will be censored at the date of last known date patient alive.

14.1.3.2.3 Time to progression

Some studies might consider only death related to underlying cancer as an event which indicates progression. In this case the variable “Time to progression” might be used. TTP is defined as PFS except for death unrelated to underlying cancer.

Time to progression (TTP) is the time from date of randomization/start of treatment to the date of event defined as the first documented progression or death due to underlying cancer. If a patient has not had an event, time to progression is censored at the date of last adequate tumor assessment.

14.1.3.2.4 Time to treatment failure

This endpoint is often appropriate in studies of advanced disease where early discontinuation is typically related to intolerance of the study drug. In some protocols, time to treatment failure may be considered as a sensitivity analysis for time to progression. The list of discontinuation reasons to be considered or not as treatment failure may be adapted according to the specificities of the study or the disease.

Time to treatment failure (TTF) is the time from date of randomization/start of treatment to the earliest of date of progression, date of death due to any cause, or date of discontinuation due to reasons other than ‘Protocol violation’ or ‘Administrative problems’. The time to treatment failure for patients who did not experience treatment failure will be censored at last adequate tumor assessment.

14.1.3.2.5 Duration of response

The analysis of the following variables should be performed with much caution when restricted to responders since treatment bias could have been introduced. There have been reports where a treatment with a significantly higher response rate had a significantly shorter duration of response but where this probably primarily reflected selection bias which is explained as follows: It is postulated that there are two groups of patients: a good risk group and a poor risk group. Good risk patients tend to get into response readily (and relatively quickly) and tend to remain in response after they have a response. Poor risk patients tend to be difficult to achieve

a response, may have a longer time to respond, and tend to relapse quickly when they do respond. Potent agents induce a response in both good risk and poor risk patients. Less potent agents induce a response mainly in good risk patients only. This is described in more detail by [Morgan \(1988\)](#).

It is recommended that an analysis of all patients (both responders and non-responders) be performed whether or not a “responders only” descriptive analysis is presented. An analysis of responders should only be performed to provide descriptive statistics and even then interpreted with caution by evaluating the results in the context of the observed response rates... If an inferential comparison between treatments is required this should only be performed on all patients (i.e. not restricting to “responders” only) using appropriate statistical methods such as the techniques described in [Ellis et al \(2008\)](#). It should also be stated in the protocol if duration of response is to be calculated in addition for unconfirmed response.

For summary statistics on “responders” only the following definitions are appropriate. (Specific definitions for an all-patient analysis of these endpoints are not appropriate since the status of patients throughout the study is usually taken into account in the analysis).

Duration of overall response (CR or PR): For patients with a CR or PR (which may have to be confirmed the start date is the date of first documented response (CR or PR) and the end date and censoring is defined the same as that for time to progression.

The following two durations might be calculated in addition for a large Phase III study in which a reasonable number of responders is seen.

[figure not shown]
Duration of overall complete response (CR): For patients with a CR (which may have to be confirmed) the start date is the date of first documented CR and the end date and censoring is defined the same as that for time to progression.

Duration of stable disease (CR/PR/SD): For patients with a CR or PR (which may have to be confirmed) or SD the start and end date as well as censoring is defined the same as that for time to progression.

14.1.3.2.6 Time to response

Time to overall response (CR or PR) is the time between date of randomization/start of treatment until first documented response (CR or PR). The response may need to be confirmed depending on the type of study and its importance. Where the response needs to be confirmed then time to response is the time to the first CR or PR observed.

Although an analysis on the full population is preferred a descriptive analysis may be performed on the “responders” subset only, in which case the results should be interpreted with caution and in the context of the overall response rates, since the same kind of selection bias may be introduced as described for duration of response in [Section 14.1.3.2.4](#). It is recommended that an analysis of all patients (both responders and non-responders) be performed whether or not a “responders only” descriptive analysis is presented. Where an inferential statistical comparison is required, then all patients should definitely be included in the analysis to ensure the statistical test is valid. For analysis including all patients, patients who did not achieve a response (which may have to be a confirmed response) will be censored using one of the following options.

- at maximum follow-up (i.e. FPFV to LPLV used for the analysis) for patients who had a PFS event (i.e. progressed or died due to any cause). In this case the PFS event is the worst possible outcome as it means the patient cannot subsequently respond. Since the statistical analysis usually makes use of the ranking of times to response it is sufficient to assign the worst possible censoring time which could be observed in the study which is equal to the maximum follow-up time (i.e. time from FPFV to LPLV)
- at last adequate tumor assessment date otherwise. In this case patients have not yet progressed so they theoretically still have a chance of responding

Time to overall complete response (CR) is the time between dates of randomization/start of treatment until first documented CR. Similar analysis considerations including (if appropriate) censoring rules apply for this endpoint described for the time to overall response endpoint.

14.1.3.2.7 Definition of start and end dates for time to event variables

Assessment date

For each assessment (i.e. evaluation number), the **assessment date** is calculated as the latest of all measurement dates (e.g., X-ray, CT-scan) if the overall lesion response at that assessment is CR/PR/SD/UNK. Otherwise - if overall lesion response is progression - the assessment date is calculated as the earliest date of all measurement dates at that evaluation number.

In the calculation of the assessment date for time to event variables, any unscheduled assessment should be treated similarly to other evaluations.

Start dates

For all “time to event” variables, other than duration of response, the randomization/ date of treatment start will be used as the start date.

For the calculation of duration of response the following start date should be used:

- Date of first documented response is the assessment date of the first overall lesion response of CR (for duration of overall complete response) or CR / PR (for duration of overall response) respectively, when this status is later confirmed.

End dates

The end dates which are used to calculate ‘time to event’ variables are defined as follows:

- Date of death (during treatment as recorded on the treatment completion page or during follow-up as recorded on the study evaluation completion page or the survival follow-up page).
- Date of progression is the first assessment date at which the overall lesion response was recorded as progressive disease.
- Date of last adequate tumor assessment is the date the last tumor assessment with overall lesion response of CR, PR or SD which was made before an event or a censoring reason occurred. In this case the last tumor evaluation date at that assessment is used. If no post-baseline assessments are available (before an event or a censoring reason occurred) the date of randomization/start of treatment is used.

- Date of next scheduled assessment is the date of the last adequate tumor assessment plus the protocol specified time interval for assessments. This date may be used if back-dating is considered when the event occurred beyond the acceptable time window for the next tumor assessment as per protocol (see [Section 14.1.3.2.7](#)).

Example (if protocol defined schedule of assessments is 3 months): tumor assessments at baseline - 3 months - 6 months - missing - missing - PD. Date of next scheduled assessment would then correspond to 9 months.

- Date of discontinuation is the date of the end of treatment visit.
- Date of last contact is defined as the last date the patient was known to be alive. This corresponds to the latest date for either the visit date, lab sample date or tumor assessment date. If available, the last known date patient alive from the survival follow-up page is used. If no survival follow-up is available, the date of discontinuation is used as last contact date.
- Date of secondary anti-cancer therapy is defined as the start date of any additional (secondary) antineoplastic therapy or surgery.

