10.4.3 Handling of missing values/censoring/discontinuations

Part 1: Safety run-in

Subjects who are ineligible for the DDS will be excluded from the primary analysis (incidence of DLT during first 8 weeks of PDR001 in combination with dabrafenib and trametinib), although their data will be used for all remaining analyses.

Other missing data will simply be noted as missing on appropriate tables/listings.

Part 2: Biomarker cohort

Missing data will simply be noted as missing on appropriate tables/listings.

Part 3: Double-blind, randomized, placebo-controlled part

In the primary analysis, PFS will be censored at the date of the last adequate tumor assessment if no PFS event is observed prior to the analysis cut-off date.

PFS events documented after the initiation of new anti-neoplastic therapy (i.e. RECIST 1.1 documented disease progression or death) will be considered for the primary analysis provided tumor assessments continue after initiation of new cancer therapy.

If a PFS event is observed after two or more missing or non-adequate tumor assessments, then PFS will be censored at the last adequate tumor assessment before the PFS event. If a PFS event is observed after a single missing or non-adequate tumor assessment, the actual date of event will be used (RECIST 1.1 in [Appendix 1](#)).

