The DMC recommendation at the interim PFS analysis will be based on whether the predefined efficacy threshold for primary endpoint PFS by investigator was met and will also take into account PFS results by central radiology review. The details on criteria used will be provided in the DMC charter.

If the DMC recommendation is to consider making the unblinded results available, key Novartis personnel will review the (unblinded) interim data and make the final decision on what steps to take. Full details of this decision-making process including who will have access to the unblinded results will be specified in the DMC Charter.

The projected timing of the interim and final PFS analysis based on current study data is summarized in [Table 10-1](#). However, note that due to the limited follow-up the predictions for timing of analyses is highly uncertain. Indeed, doublet data from two pivotal randomized Phase

III studies (MEK115306 [COMBI-d]) and MEK116513 [COMBI-v]) indicate that there could be a rapid reduction in the event rate with longer follow-up which would lead to the targeted events occurring much later than predicted from the current study data alone.

Table 10-1 Estimated timelines for interim and final PFS analyses

Months after randomization of the first patient (prediction based on actual study data at Protocol Amendment 5)	# PFS Events (information fraction)	Cumulative PFS Power against a hazard ratio of 1 for first x months and a hazard ratio 0.60 after x months	
		x = 3 months Delayed Effect	x = 5 months Delayed Effect
19	260 (74%)	41.5%	15.5%
25	352 (100%)	93.8%	80.6%

Calculated using EAST 6.4

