14.1.2.1 Definitions

14.1.2.1.1 Disease measurability

In order to evaluate tumors throughout a study, definitions of measurability are required in order to classify lesions appropriately at baseline. In defining measurability, a distinction also needs to be made between nodal lesions (pathological lymph nodes) and non-nodal lesions.

- **Measurable disease** - the presence of at least one measurable nodal or non-nodal lesion. If the measurable disease is restricted to a solitary lesion, its neoplastic nature should be confirmed by cytology/histology.

For patients without measurable disease see [Section 14.1.3.2.8](#).

Measurable lesions (both nodal and non-nodal)

- **Measurable non-nodal** - As a rule of thumb, the minimum size of a measurable non-nodal target lesion at baseline should be no less than double the slice thickness or 10mm whichever is greater - e.g., the minimum non-nodal lesion size for CT/MRI with 5mm cuts will be 10 mm, for 8 mm contiguous cuts the minimum size will be 16 mm.
- **Lytic bone lesions or mixed lytic-blastic lesions with identifiable soft tissue components**, that can be evaluated by CT/MRI, can be considered as measurable lesions, if the soft tissue component meets the definition of measurability.
- **Measurable nodal lesions (i.e. lymph nodes)** - Lymph nodes ≥ 15 mm in short axis can be considered for selection as target lesions. Lymph nodes measuring ≥ 10 mm and < 15 mm are considered non-measurable. Lymph nodes smaller than 10 mm in short axis at baseline, regardless of the slice thickness, are normal and not considered indicative of disease.

- Cystic lesions:
 - Lesions that meet the criteria for radiographically defined simple cysts (i.e., spherical structure with a thin, non-irregular, non-nodular and non-enhancing wall, no septations, and low CT density [water-like] content) should not be considered as malignant lesions (neither measurable nor non-measurable) since they are, by definition, simple cysts.
 - ‘Cystic lesions’ thought to represent cystic metastases can be considered as measurable lesions, if they meet the definition of measurability described above. However, if noncystic lesions are present in the same patient, these are preferred for selection as target lesions.

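### The definition of an adequate tumor assessment omits Non-CR/Non-PD, and the promised rule for subjects without measurable disease is absent, so later PFS events in such subjects would be censored

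*Protocol*

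**What the plan says.** The adequacy definition is in Section 14.1.3.2.7: "Date of last adequate tumor assessment is the date the last tumor assessment with overall lesion response of CR, PR or SD". The same section dates an assessment by the latest measurement when the response is CR, PR, SD or UNK, and by the earliest when it is progression. No other response is given a date. Its fallback reads: "If no post-baseline assessments are available (before an event or a censoring reason occurred) the date of randomization/start of treatment is used".

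Section 10.4.3 uses this definition twice. Subjects without an event are censored at the last adequate assessment. For events: "If a PFS event is observed after two or more missing or non-adequate tumor assessments, then PFS will be censored" (at the last adequate assessment before the event), whereas "If a PFS event is observed after a single missing or non-adequate tumor assessment, the actual date of event will be used".

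Section 14.1.3.1, in defining clinical benefit rate, refers to "an overall lesion response of SD or Non-CR/Non-PD which lasts for a minimum time duration". Non-CR/Non-PD is therefore recognised as an overall response and not only as a non-target one.

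On subjects without measurable disease, Section 14.1.2.1.1 says "For patients without measurable disease see" Section 14.1.3.2.8, and Section 14.1.3 says that section "outlines the special considerations that need to be given to patients with no measurable disease at baseline".

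Section 10.4.4 applies the primary analysis conventions to PFS by central review. Section 10.7.1 says the DMC recommendation at the interim "will also take into account PFS results by central radiology review".

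**The concern.** A subject with only non-target disease cannot have PR or SD, because both rest on the sum of target-lesion diameters. While the disease persists without unequivocal worsening, the natural read is Non-CR/Non-PD. That scan is evaluable and shows the subject to be progression-free, yet the definition gives it the standing of a missing scan.

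Two things are then lost: progressions and deaths that follow two or more such scans, and the follow-up of subjects who remain event-free. The more likely place is central review. A central reader may select different lesions from the investigator and could select none. Under the shared conventions, central-review PFS could then differ from investigator PFS for a reason unrelated to the tumor.

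**Working it through.** **The texts side by side**

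- Adequate (14.1.3.2.7): CR, PR, SD. Dated (14.1.3.2.7): CR, PR, SD, UNK, progression. Recognised as an overall response (14.1.3.1): also Non-CR/Non-PD. That category is in neither of the first two lists.
- Table 14-3 has a footnote for subjects with no non-target lesions, and Section 14.1.4.5.4 also covers them. Neither covers subjects with no target lesions.
- Section 14.1.3.2.8 is headed Sensitivity analyses and contains no rule for non-measurable disease. Other pointers in the appendix run one number low: definitions in 14.1.3.2.7 are cited as 14.1.3.2.6, and duration of response in 14.1.3.2.5 is cited as 14.1.3.2.4. Moving this pointer up by one gives 14.1.3.2.9, which does not exist, since Section 14.1.4 follows directly.

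**Which events are affected**

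Table 7-4 puts the first scan at C4D1 (3 × 28 days = week 12), then every 8 weeks: 20, 28, 36 and so on. For a subject read as Non-CR/Non-PD until progression:

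| Progression first seen | Non-adequate scans before it | Result under 10.4.3 |
|---|---|---|
| Week 12 | 0 | Event counts |
| Week 20 | 1 | Event counts at its actual date |
| Week 28 or later | 2 or more | Censored at a last adequate assessment that does not exist |

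**The plan's event target**

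Inputs from Sections 10.7.1 and 10.8: average HR 0.739, one-sided 2.5%, 80% power, 1:1 allocation, 352 events, 532 randomized, control median 11 months, and a final one-sided threshold of 0.02483.

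- Schoenfeld: 4(1.960 + 0.842)² / (ln 0.739)² gives 344 events; Freedman gives 349. Both are within 3% of 352.
- 352/532 = 66.2% of subjects with an event.

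**Size**

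With an exponential curve, week 20 = 20 × 12/52.18 = 4.60 months. The cumulative event proportion is 1 − 0.5^(4.60/11) = 25.2% (16.0% at week 12). The plan assumes HR = 1 for the first 5 months, so this holds in both arms.

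Share of events kept in affected subjects: 25.2/66.2 = 38%. Share lost: 62%.

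The proportion q with no target lesions is not in the protocol, so a range is assumed. Events lost = 352 × q × 0.62. Power = Φ(|ln 0.739| × √d / 2 − z), with d the remaining events and z the normal quantile for 0.02483.

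| Assumed q | Subjects (532q) | Their events (352q) | Events lost | Power (0.809 at 352) |
|---|---|---|---|---|
| 1% | 5 | 3.5 | 2 | 0.807 |
| 2% | 11 | 7.0 | 4 | 0.804 |
| 5% | 27 | 17.6 | 11 | 0.797 |
| 10% | 53 | 35.2 | 22 | 0.784 |

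This assumes that no affected subject reaches CR and that event counts are near 352. That number is the target for the investigator-based test; central-review PFS has no event target. The power column therefore only gives scale, for the case where the primary analysis itself were affected.

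**The case against.** The strongest case is that this is a drafting gap with a visible intention. Section 14.1.4.5.6 illustrates the lack of adequate assessments with UNK reads just before cut-off, so adequate seems to mean evaluable. Table 14-3 never yields Non-CR/Non-PD at the overall level. The term appears as an overall response only in the clinical benefit rate definition, and that rate is not an endpoint here. On this view the response of a no-target subject is undefined, not declared non-adequate. Appendix 1 is general guidance to be adapted for each study, and the SAP and the independent review charter, which are not shown, may settle it. This stands as a reason to expect that the program did something sensible. It does not repair the text, which lists the adequate categories without this one and promises a rule that is missing.

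A reader might infer more than the documents support:

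- **That affected subjects are censored at randomization.** The fallback is worded for the absence of any post-baseline assessment. These subjects have assessments, so the date is undefined unless the fallback is extended to them.
- **That every progression in them is lost.** Those at week 12 or 20 count. A subject whose lesions all disappear has a CR, which is adequate.
- **That the primary result is affected.** The primary test uses investigator assessment. Eligibility is in the part of the protocol not shown, and nothing shown says that subjects without investigator target lesions were enrolled, or how often a central reader selected none.
- **That the hazard ratio is biased in a known direction.** Nothing in the documents shows this.

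**Conclusion.** The point holds as a defect in a stated rule. Followed literally, Sections 14.1.3.2.7 and 10.4.3 discard PFS events that come after two or more Non-CR/Non-PD scans, give no credit for event-free follow-up in those subjects, and leave the censoring date undefined.

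The likely size is small: about 2 to 22 events if 1% to 10% of subjects have no target lesions, and none if there are no such subjects. The prevalence is assumed throughout. If every subject has investigator target lesions, the effect is confined to central-review PFS. That analysis is supportive, although the DMC also considers it at the interim, where the efficacy threshold itself is set on investigator PFS.

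**What to change.** - In Section 14.1.3.2.7, add Non-CR/Non-PD to the definition of the last adequate assessment and to the responses dated by the latest measurement.
- In Table 14-3, add rows for subjects with no target lesions. Without a new lesion: non-target CR gives CR, Non-CR/Non-PD gives Non-CR/Non-PD, and UNK gives UNK. Non-target PD or any new lesion gives PD.
- In Sections 14.1.2.1.1 and 14.1.3, point to those rows instead of Section 14.1.3.2.8.
- Confirm how the PFS program treated Non-CR/Non-PD reads, by investigator and by central review. If any event or follow-up was dropped, report the number by arm and show the affected estimate both ways, labelled as a correction made after the results were known.

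The text changes are a few words and three or four table rows, with no effect on the event target. The protocol records that the final PFS analysis is complete and that RECIST data are no longer collected, so the real work is the check of the program, plus a documented re-run only if reads were lost.
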